Our preclinical data set for algorithm training required approximatively 300 data points from 20 sheep. We expect that a similar amount of human data sets will be required for algorithm training and then another 10 human subjects will be enrolled for prospective algorithm validation of the LUMERAH device. Therefore, the absolute *minimum* required sample size to compare Nellcor N-400 device output to the LUMERAH output is 30 subjects. However, we will calibrate and validate on up to 60 patients to ensure that we can identify hypoxic fetuses. East et al²⁴ reported that 3.9% of observations with the Nellcor N-400 technology displayed fetal oxygen saturations below 30%. Therefore, enrolling and following 60 subjects allows the opportunity to monitor and study approximately two hypoxic fetuses. We intend to collect up to 60 of these "ground truth" cases with varied oxygenation levels before proceeding to PILOT 2. With the expectation that we will have to consent an additional 50% who may not meet the inclusion/exclusion criteria, the total number consented will be a maximum of 90 subjects.

17. Data Management

Only individuals approved by the Sponsor and who have adequate training in the use of the Investigational device are given authorization of access to perform the measurement and record the data. The data collected will be marked with a study ID number to protect confidentiality of each subject.

Only the research staff will have access to the link between the study ID and the patient's identifying information. The key will be stored in a password-protected document on a restricted access folder on the hospital network. Only the PI/Co-I and research team will have access to this document.

A separate document listing only study ID numbers will be stored on a password-protected document on a restricted access folder on the hospital network. This will contain the subjects' de-identified obstetric and medical history as relevant for the project. Data will be submitted to the sponsor through an electronic, secure database.

18. Study Monitoring

This study will be monitored for data accuracy and adherence to the protocol by the Sponsor's representative and/or a 3rd party qualified monitor. It is expected that there will be frequent attendance of the Sponsor's representative at the study site. Major protocol deviations will be reported to the Sponsor immediately and the IRB at the required reporting intervals.

19. Regulatory Requirements

Due to the non-significant risk determination by the Sponsor, this study is subject to the abbreviated requirements set forth by CFR 21 Part 812.2(b), 21CFR Part 50 (Informed Consent), and 21CFR Part 56

VERSION DATE: 9/8/21

(IRB Review). The manufacturer of the device developed a data collection unit that gathers light that is reflected from in-utero fetuses. It should be noted that as an experimental device, the Investigational device has not been tested at NRTL registered testing facilities. This is common practice during the early stages of medical device development.

20. Personnel Responsibilities

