The LUMERAH device has undergone accuracy testing using pregnant sheep whereby the oxygenation of the sheep fetus can be manipulated and measured by taking periodic fetal blood samples. This cannot be done in the human model as it carries too much risk to both the mother and the baby; therefore, the Sponsor used the previously approved fetal oxygen sensor made by Nellcor to manufacture new sensors, the new sensors are now being manufactured by Axcesor. The Nellcor sensor was considered to be very accurate and underwent a great deal of scientific rigor before submitting all of the clinical and regulatory documents to the FDA. There were over 50 scientific papers published on the utility of the device. After the company was sold to Tyco, it was then sold to Covidien, then to Medtronic and during that time, they let the approval with the FDA lapse in 2017. The device was not as user-friendly as the proposed investigational device but because of its accuracy, the Nellcor device is necessary to use as the "ground truth" during this study. In other words, before we train the algorithm of the less-invasive LUMERAH device, we want to be sure that it is as accurate as possible and the only way to do that is by using internal sensors. To obtain these devices, Raydiant Oximetry (made up of mostly ex-Nellcor employees) either had devices or contacted prior investigators from the Nellcor studies. These older Nellcor sensors will be used as samples, the new single-use internal sensors are now being manufactured by Axcesor. The benefit/risk analysis supports using a prior FDA approved product (Nellcor System) that is no longer marketed with new manufactured internal sensors vs invasive blood sampling of a fetus in-utero.

2. Objectives

The objectives of this study are as follows: 1) Assess the LUMERAH device specificity in the prediction of newborn metabolic acidosis as an adjunct to cardiotocography; 2) Assess human factors, device usability factors, and signal capture relative to subject factors (e.g., BMI, device position, maternal movement, etc.); and 3) Compare Nellcor N-400 device output to the LUMERAH output.

3. Study Design, Recruitment Methods, Investigator/Team Training and Timeline

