The device shipments/delivery and request for return will be the responsibility of the Sponsor. The device is not delivered to the site until IRB approval has been obtained. The Investigational device is precommercialization and will not be available to study subjects after participation in the study. Study subjects will not be restricted from use of any medication or other substance while participating in the study. In addition to the PI and co-investigators, members of the Raydiant Oximetry team may transport and be accountable for the investigational device.

10. Data Collection

In addition to specific LUMERAH device and cardiotocography data, the following data is the minimum subject data set to be collected during this study:

- Maternal demographics such as race, ethnicity, age, parity, prior perinatal outcomes, height, weight (to calculate BMI), number and date of prior cesarean deliveries, Maternal Vital Signs such as the maternal heart rate and maternal oxygen saturation.
- CTG Tracings to be downloaded from the EMR
- Location on maternal abdomen for best signal quality
- Safety data (see "Adverse Event Reporting" below)

In addition, the internal sensor data will be analyzed and compared to the LUMERAH device data. We will report the mean error, standard deviation of difference and root-mean square error from the study results. In addition, we will present a scatter plot (with the identity line and Deming regression line), a Bland-Altman plot [with the 95% limits of agreement (LoA)] and report the repeatability and reproducibility by providing a population mean bias (μ 0), between-subject variance (σ 2) with our final statistical analyses.

Neonatal outcomes will not be collected during this study.

11. Risks to Subjects/NSR Determination

A significant-risk (SR) device study is defined by the United States Food and Drug Administration (https://www.fda.gov/media/75459/download) as one that:

- Is intended as an implant and presents a potential for serious risk to the health, safety, or welfare of a subject;
- Is purported or represented to be for use supporting or sustaining human life and presents a potential for serious risk to the health, safety, or welfare of a subject;
- Is for a use of substantial importance in diagnosing, curing, mitigating, or treating disease, or otherwise preventing impairment of human health and presents a potential for serious risk to the health, safety, or welfare of a subject;

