This is an observational, noninvasive study with primary endpoints related to the LUMERAH device correlation with the Nellcor device and internal sensor (manufactured by Axcesor). Raydiant Oximetry met with the FDA on Feb 11, 2020 and suggested that we power our pilot and pivotal studies for specificity, and not sensitivity, because poor specificity of CTG technology is the unmet clinical need in obstetrics. CTG technology has a 29% specificity and the FDA agreed with this approach. Seelbach-Gobel²³ demonstrated that the Nellcor fetal pulse oximetry device had a specificity of 65% for the detection of newborn metabolic acidosis. The incidence of newborn metabolic acidosis has been reported to be 2-4% and the incidence of hypoxic fetuses is 3-4%. Our sample size calculations are based on a significance level of 0.05 (i.e. type 1 error=0.05) with the goal to achieve power of 0.8 and a lower confidence level of 80% to establish a clinical proof of concept. The sample size calculation, under these assumptions, is 48 subjects for this pilot study.

VERSION DATE: 9/8/21

To compare the Nellcor N-400 device output to the LUMERAH output, we are following the FDA guidance document (dated March 4, 2013) for pulse oximeters, where the in-vivo validation set should include at least 200 data points from 10 or more human subjects. Per the FDA recommendation, we will report the root mean square (RMS) error and produce a scatter plot with the identity line and a Deming regression line. In addition, we will report a Bland-Altman plot with the 95% limits of agreement as well as the 95% confidence intervals for the limits of agreement.

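### Objective 1 (specificity for newborn metabolic acidosis) cannot be answered because neonatal outcomes are not collected, and the 48-subject power statement belongs to no defined analysis

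*Combined protocol and SAP*

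**What the plan says.** Section 2 (Objectives) lists first: "Assess the LUMERAH device specificity in the prediction of newborn metabolic acidosis as an adjunct to cardiotocography". The Study Synopsis states objective 1 differently, as safety and performance of the device, and mentions neither specificity nor acidosis.

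Section 10 (Data Collection) says: "Neonatal outcomes will not be collected during this study". Neither its minimum data set nor the schedule in Section 3 contains a cord gas, pH or base deficit. Under Section 7, participation ends after at most 6 hours of active labor.

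Section 16 (Statistical Considerations) reports that at an FDA meeting the sponsor "suggested that we power our pilot and pivotal studies for specificity, and not sensitivity", and that the FDA agreed. It states that "CTG technology has a 29% specificity" and that, in a published study, the Nellcor device "had a specificity of 65% for the detection of newborn metabolic acidosis". It then gives incidences for two conditions: 2-4% for newborn metabolic acidosis and 3-4% for hypoxic fetuses. The calculation uses a significance level of 0.05 "with the goal to achieve power of 0.8 and a lower confidence level of 80% to establish a clinical proof of concept". It concludes: "The sample size calculation, under these assumptions, is 48 subjects for this pilot study".

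The primary efficacy endpoint in the synopsis is concurrence with the Nellcor N-400; Section 16 calls it correlation. Section 16 supports that comparison separately: at least 200 data points from 10 or more subjects, a minimum of 30 subjects, and up to 60.

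**The concern.** Specificity is the proportion of newborns without acidosis whom the device calls negative. Its denominator cannot be formed without each newborn's acid-base status, which the protocol declines to record.

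The power statement has a related fault. The sentence giving 48 names no target condition. There are two readings:

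- **Newborn metabolic acidosis.** This is the likelier reading, because the 65% is cited for it. The power cannot exist, since the outcome is not collected.
- **Fetal hypoxia** (saturation below 30% against Nellcor). The reference is recorded, but the plan defines no specificity endpoint, no LUMERAH positivity rule and no specificity analysis.

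On either reading, the study would end with a listed first objective that has no result and a claim of 80% power that no analysis uses. Readers of the synopsis and of Section 2 would also expect different results.

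**Working it through.** **1. Trying to reproduce the 48.** Inputs from Section 16: p0 = 0.29 (CTG) and p1 = 0.65 (Nellcor), alpha = 0.05, power = 0.8. The plan labels neither proportion as null or alternative; these are the only candidates it offers. z_a = 1.645 (one-sided) or 1.960 (two-sided); z_b = 0.842.

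- *One sample:* n = [(z_a·√(p0(1−p0)) + z_b·√(p1(1−p1))) / (p1−p0)]², with √0.2059 = 0.454, √0.2275 = 0.477 and difference 0.36.
  - One-sided: [(1.645×0.454 + 0.842×0.477)/0.36]² = 10.2, so 11.
  - Two-sided: 12.9, so 13.
- *Two independent groups,* pooled proportion 0.47: n per group = [(z_a·√(2×0.47×0.53) + z_b·√(0.2059+0.2275)) / 0.36]².
  - One-sided: 22.7, so 23 per group and 46 in total.
  - Two-sided: 29.0, so 29 per group and 58 in total.
- *Paired comparison with CTG in the same women (McNemar):* n = [z_a·√ψ + z_b·√(ψ−0.36²)]² / 0.36², where ψ is the total discordance. The plan does not give ψ; with these proportions it can run from 0.36 to 0.29 + 0.65 = 0.94.
  - One-sided: 15 to 43.
  - Two-sided: 20 to 55. A value of 48 needs ψ of about 0.83: [1.960×0.911 + 0.842×0.837]²/0.1296 ≈ 47.8.

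The one-sided two-group total divided by 0.96 is 46/0.96 = 47.9, which rounds to 48. However, the plan states no such step, and a single cohort has no second group. The role of the lower confidence level of 80% is not explained either. The 48 is therefore neither confirmed nor shown wrong.

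**2. Subjects evaluable for objective 1.** With no neonatal outcomes collected, the number with a known acidosis status is 0 of 48, or 0 of 60. Had it been collected, the specificity denominator at the plan's incidence would be 48 × 0.98 = 47.0 to 48 × 0.96 = 46.1 newborns.

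**3. The hypoxia reading.** Section 16 applies its 3.9%, a rate per observation, to subjects. Doing the same gives 60 × 0.039 = 2.3 hypoxic fetuses and 57.7 (about 58) non-hypoxic ones. A denominator would exist, but no analysis is defined on it.

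**4. What is planned against what specificity needs.** Sections 10 and 16 list mean error, standard deviation of the difference, root-mean-square error, a scatter plot with Deming regression, a Bland-Altman plot with limits of agreement, population mean bias and between-subject variance. All describe agreement of continuous readings. A specificity analysis needs a target condition, a device cut-off, a two-by-two table and a hypothesis or interval. None is given.

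**The case against.** The best defence is the hypoxia reading: the reference is recorded, and the protocol already uses saturation below 30% as the marker of hypoxia. That is so, but it supplies neither a LUMERAH decision rule nor an analysis, and it would not answer Section 2, which names newborn acidosis.

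It can also be said that infants receive their own identifiers, that the data set is described as a minimum, and that adverse events are reported. None of these supplies acid-base status, and none overrides an explicit statement that neonatal outcomes will not be collected.

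A fair point concerns the remedy. The synopsis does not automatically outrank Section 2, and Section 16 reports FDA agreement to power for specificity. The sponsor could instead collect acid-base status and define the analysis. That route is open, but it adds data collection to a study that has chosen to do without it. The reported agreement does not create an outcome that is not recorded.

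A paired comparison with CTG is a natural design for this cohort and needs no second group. It reaches 48 only at a high discordance that the plan does not state, so it leaves the 48 unexplained.

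One limit stands in full. Being listed first does not make objective 1 primary, and 48 lies within the planned 30 to 60, so enrolment need not change.

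**Conclusion.** The concern holds. Objective 1 in Section 2 and the exclusion in Section 10 cannot both stand: 0 of up to 60 subjects will have the reference status. The statement of 48 subjects at 80% power is attached to no defined analysis on either reading of the target condition. The first conclusion rests on the text alone. The second rests on the absence of any specificity analysis in Sections 10 and 16.

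No claim is made that 48 is miscalculated. The recomputations assume 29% as the null and 65% as the alternative, which the plan does not say.

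This should be fixed, but it does not threaten the study. Agreement with Nellcor remains the primary endpoint, and its sample-size basis is unaffected.

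**What to change.** - Replace objective 1 in Section 2 with the synopsis wording on safety and performance.
- In Section 16, delete the specificity power statement and the 48, or label them as planning for a later study.
- Rest the sample size on the agreement rationale already in Section 16 (200 points from at least 10 subjects, minimum 30, up to 60).
- If a specificity measure is wanted from the recorded data, define it as exploratory: LUMERAH against Nellcor for saturation below 30%, described as fetal hypoxia and not newborn acidosis. State the LUMERAH positivity rule, allow for clustering of readings by subject, and make no power claim. Restrict it to the validation subjects (10 at the plan's minimum), because the algorithm is trained on the others.

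The cost is protocol wording, submitted to the IRB as an amendment under Section 20.1. Enrolment, procedures and the primary analysis do not change. The plan gives up a claim of 80% power for specificity that it could not deliver. Keeping the acidosis objective would instead require collecting newborn acid-base status and specifying the analysis, which costs more.

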VERSION DATE: 9/8/21

STUDY TITLE:

Trans-abdominal fetal pulse oximetry: PILOT 1

STUDY SPONSOR:

Raydiant Oximetry, Inc. [name]

Version No.	Version Date	Modifications
V1	3/15/21	N/A- Original Release
V2	4/9/21	Added exclusion criteria to correspond
		with Nellcor IFU
V3	6/7/21	Clarification of inclusion induction/active
		labor enrollment, timing& removal device,
		Amazon card replaced with UTMB
		Clincard, defined health provider
		(physician, midwife, nurse practitioner,
		nurse)
V4	7/14/21	Additional clarifications added in the
		Background, Procedures, and Risks
		Sections.
		Added that internal sensor previously
		manufactured by Nellcor, is now
		manufactured by Axcesor. Clarification on
		enrollment and sensor comparison
		statistics.
V5	9/8/21	Remove reference to sterile sleeve, replace
		words to indicate internal sensor is
		sterilized.

VERSION DATE: 9/8/21

Study Synopsis

Title: Trans-abdominal fetal pulse oximetry; PILOT 1

Study Design: Prospective, observational, investigator-blinded study.

Study Device: The Raydiant Oximetry Sensing System (LUMERAH)

Objectives: 1) Assess safety and performance of the LUMERAH device as an adjunct to cardiotocography; 2) Assess human factors, device usability factors, and signal capture; and 3) Compare device output to "ground truth" technology (Nellcor N-400 with internal sensors manufactured by Axcesor).

Safety Endpoints

Rate of device-related adverse events such as erythema or rash on the maternal abdomen at the location of the sensor. Note: In this study, use of the device provides additional clinical information, but clinical judgement is based on standard fetal monitoring, including cardiotocography, and investigators are blinded to oximetry readings. The maternal skin at the sensor site will be examined intra and postpartum.

Effectiveness Endpoints

Primary efficacy endpoint is concurrence of oximetry readings compared to those of the Nellcor N400 System ("ground truth").

Study Populations:

Up to 60 pregnant women. who are/have:

- 1) Willing and capable to provide informed consent
- 2) Age \geq 18 years
- 3) BMI < 50 (with no more than 4 cm between maternal skin and fetal skin)
- 4) Gestational age > 36 weeks
- 5) Singleton pregnancy
- 6) Vertex presentation
- 7) Active labor
- 8) Category I or Category II tracings
- 9) Ruptured amniotic sac with cervical dilation of ≥ 2 cm and a station of -2 or lower

Exclusion Criteria

- 1) Age < 18 years

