- 8) Category I or Category II tracings
- 9) Ruptured amniotic sac with cervical dilation of ≥ 2 cm and a station of ≤ 2 or lower

VERSION DATE: 9/8/21

Exclusion Criteria:

- 1) Age <18 years
- 2) BMI > 50 third trimester
- 3) Gestational age < 36 weeks
- 4) Multiple gestation
- 5) Nonvertex fetal presentation
- 6) Suspected vasa previa
- 7) Latent labor
- 8) Category III CTG tracing (i.e., need for immediate delivery)
- 9) Fetal anomalies and/or chromosomal disorders
- 10) Chorioamnionitis
- 11) Placenta Previa
- 12) History of HIV, Genital Herpes, or other infection precluding internal monitoring
- 13) Unable to provide informed consent (e.g., cognitively impaired)

5. Withdrawal of Subjects

Subjects will be withdrawn from the study if, after obtaining informed consent, the subject no longer meets the inclusion/exclusion criteria or if the pregnancy is no longer a normal pregnancy, e.g., if there are health risks to mother or fetus or both. If subjects self-withdraw from the study, any data abstracted from the investigational device up until that point will be used in data analysis. No further measurements or data will be collected after withdrawal. The study involves measurement of the fetal pulse signal with the investigational device during labor. The study does not involve any drugs or evaluative X-ray and no additional safety precautions or follow up will need to be taken if a subject withdraws from the study.

6. Consent process

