Subjects will be consented upon admission to the labor and delivery unit in a private setting. Upon admission to labor and delivery, information will be delivered orally and in writing. If a patient agrees to participate at this time, consent will be obtained. It is assumed that at least 50% additional subjects (for a total of up to 90 subjects) will be initially consented compared to the number actually completing the study due to the inclusion/exclusion criteria that cannot be fully ascertained upon admission. In addition, a subject may originally consent to the study but change her mind once labor begins. The *i*nformed consent process will not be rushed and subjects will be informed that their participation is voluntary and there will be no change in their medical care if they choose not to participate. Investigators will describe the safe, noninvasive nature of this study, as well as the future benefit to women and their fetuses if measurement of fetal oxygenation can be performed. Subjects will be invited to ask questions, provide comments, or can choose to withdraw from participation at any time. A copy of the signed Informed Consent Form will be provided to each subject who chooses to participate.

Subjects who agree to participate and who complete participation (defined as device placement and monitoring) will receive a \$150 UTMB Clincard.

7. Duration of Subject Participation

Following consent and baseline data collection, subjects are expected to actively participate in the study for up 6 hours (active labor stage). Subjects end their participation in the study after that time period.

VERSION DATE: 9/8/21

8. Payment to Subjects/Cost of Participation

There is no expected cost of subject participation. Payment to the subjects who choose to participate will be set according to institutional standards.

9. Study Procedures/Device Use

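### Section 5 stops all data collection at withdrawal with no adverse-event exception, which conflicts with the planned postpartum skin check, at least for women who self-withdraw after sensor placement

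*Combined protocol and SAP*

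**What the plan says.** Section 5 (Withdrawal of Subjects) describes two routes out of the study. The first is mandated, on either of two grounds. One ground is eligibility: "Subjects will be withdrawn from the study if, after obtaining informed consent, the subject no longer meets the inclusion/exclusion criteria". The other ground concerns health and applies "if the pregnancy is no longer a normal pregnancy, e.g., if there are health risks to mother or fetus or both". The second route is the woman's own decision. Section 6 confirms that she "can choose to withdraw from participation at any time". For self-withdrawal, Section 5 says that "any data abstracted from the investigational device up until that point will be used in data analysis".

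The next sentence is the one at issue: "No further measurements or data will be collected after withdrawal". The section then notes that the study involves no drugs or X-ray, and concludes that "no additional safety precautions or follow up will need to be taken if a subject withdraws from the study". Adverse events are not mentioned anywhere in Section 5.

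The Study Synopsis, under Safety Endpoints, defines the endpoint as "Rate of device-related adverse events such as erythema or rash on the maternal abdomen at the location of the sensor". It adds: "The maternal skin at the sensor site will be examined intra and postpartum". That sentence carries no exception for women who have left the study.

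**The concern.** A postpartum skin inspection recorded after a woman has withdrawn is data collected after withdrawal. For such a woman, a site cannot follow both Section 5 and the Synopsis as written. If it follows Section 5, a woman who wore the abdominal sensor contributes exposure to the safety endpoint but has no postpartum inspection, and non-serious events noticed later are not collected.

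The endpoint affected is the only safety endpoint that the plan states. A skin reaction under the sensor is its named example, and Section 11 lists local warming, reddening and possibly rash among the effects of the LUMERAH device. An incomplete record in exposed women weakens a rate that the plan otherwise makes easy to complete.

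**Working it through.** No arithmetic applies. The check sets the sections side by side.

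**1. Can withdrawal follow sensor placement?** Yes. Section 6 allows self-withdrawal at any time. The mandated triggers in Section 5 can also arise once monitoring is under way: a Category III tracing and chorioamnionitis are both exclusion criteria in Section 4, and both can develop during labor. Women who leave before placement have no sensor site to inspect and are not affected.

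**2. What does the stop sentence cover?** Two readings are possible.

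| Reading of the stop sentence | Self-withdrawal after placement | Mandated withdrawal after placement |
|---|---|---|
| Narrow: self-withdrawal only | Conflicts with the Synopsis | Section 5 is silent; the Synopsis inspection still applies |
| General: any withdrawal | Conflicts with the Synopsis | Conflicts with the Synopsis |

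The position of the sentence, directly after the self-withdrawal rule, favors the narrow reading. Its unrestricted wording favors the general one. The conflict for self-withdrawal is present under both.

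**3. Does another section supply the missing exception?**
- The schedule in Section 3 lists adverse events as a peri-partum item, and Section 10 includes safety data in the minimum data set. Neither mentions withdrawn women.
- Section 15 requires serious adverse events associated with the investigational device to reach the IRB within 24 hours of becoming known. This is a reporting duty that starts once an event is known. It is not a rule for collecting events, and it does not reach non-serious erythema or rash.
- Section 20.2 has the sponsor investigate device-related adverse events, but an event has to be found first.

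No section permits the postpartum inspection or the collection of non-serious events after withdrawal.

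**4. What is lost?** Section 5 does not discard adverse events recorded before withdrawal, and inspection during labor may already have taken place. The loss is therefore confined to reactions first seen after withdrawal, chiefly non-serious ones.

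**5. Can the loss be sized?** That would need the number of women withdrawn after placement and the frequency, among them, of reactions first seen afterwards. The documents give neither.

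**The case against.** The strongest reply is that this is a narrow wording gap. The stop sentence follows the self-withdrawal sentence, and the closing clause speaks of a subject who withdraws, not one who is withdrawn. Its word "additional" may mean only that nothing beyond the planned procedures is required. On that view mandated withdrawals keep their postpartum inspection, and ending collection after self-withdrawal simply respects the woman's choice. Reactions to the sensor are expected to be short-lived (Section 11), so inspection during labor may catch many of them. Device-associated serious events stay reportable.

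Much of this stands, and it limits the point. It does not remove it. A woman may want monitoring to end yet be content to have her skin checked, and Section 5 gives her no such option. The softer reading of the follow-up clause does not soften the stop sentence. An unresolved ambiguity over safety data still needs a decision.

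Three stronger inferences should be resisted:
- **That Section 5 plainly ends safety collection in every withdrawn woman.** The text does not settle this.
- **That the gap between up to 90 women consented and up to 60 enrolled measures the problem.** Sections 6 and 16 attribute that gap to eligibility not yet known on admission, and Section 6 adds changes of mind once labor begins. Neither counts withdrawals after placement. Section 6 can also be read as making the 60 completers, so women withdrawn after placement may lie outside that number.
- **That the missing inspections bias the rate.** No section links the obstetric triggers for withdrawal to skin reactions.

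A separate inconsistency should not be attributed to withdrawal. Section 7 ends every woman's participation after up to 6 hours, which fits poorly with a postpartum inspection whether or not she withdraws.

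**Conclusion.** The conflict is real but limited. As written, Section 5 cancels the postpartum skin inspection and later non-serious adverse-event collection in women who self-withdraw after sensor placement. It does the same for mandated withdrawals if the stop sentence is general. What is lost is reactions first seen after withdrawal; earlier records and the reporting of device-associated serious events are untouched.

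No figure should be attached to the effect, and no direction of bias can be claimed. The conclusion rests on the wording alone, and on the premise that some women will withdraw after placement, which the documents allow for but do not count. It is worth correcting because it concerns the only stated safety endpoint and costs almost nothing. It does not threaten the comparison of the two devices.

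**What to change.** In Section 5:

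1. Limit the stop to device measurements. State that adverse-event collection and the already planned postpartum skin inspection are completed for every woman in whom a sensor was placed, unless she declines.
2. State whether the stop sentence applies to self-withdrawal only or to all withdrawals.
3. State that every woman with a sensor placed counts in the denominator of the safety rate, and report how many of them lack the postpartum inspection.
4. Reconcile Section 5 with the Synopsis, and both with Section 7, so that it is clear how a postpartum inspection fits with participation that ends after up to 6 hours.

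When monitoring stops or a device is removed is a clinical matter and is not addressed here.

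The cost is a few sentences of protocol text and an already planned skin check in the women withdrawn after placement who agree to it. Sample size, device procedures and the agreement analysis do not change.
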